In the RELAX-AHF study 1161 patients were enrolled, 1138 of whom treated with serelaxin at 30 µg/kg/day or placebo (n=568 and 570 patients, respectively). The results showed a significant relief of dyspnea as measured by change from baseline on a 100-point visual analogue scale (VAS) over 5 days ($p=0.0075$), even though dyspnea reduction as measured using a 7-point, Likert scale over the first 24 hours (primary end-points) did not achieve statistical significance. The results also showed that, compared with conventional therapy, treatment with serelaxin improved signs and symptoms of patient congestion at Day 2 and significantly reduced WHF episodes through Day 5 and the overall length of index hospital stay, associated with a range of other in-hospital clinical benefits. WHF rates were significantly decreased by serelaxin in RELAX-AHF: significantly fewer patients in the serelaxin group experienced WHF event or death through Day 5 compared with the placebo group (6.5% vs. 12.0%, OR=0.51; 95% CI: 0.33, 0.77; RLX.CHF.003; data on file). Similar results were obtained for WHF through 14 days in placebo group 15.7% (KM) and serelaxin 11.4% (KM), $p=0.024$ ([Teerlink et al 2013](#)). Serelaxin provided sustained benefits beyond the initial 48 hours of infusion leading to a clinically and statistically significant 37% reduction in the risk of both cardiovascular and all-cause-mortality through Day 180. Serelaxin had favorable effects on the short-term changes in multiple laboratory markers of cardiac, renal, and hepatic damage known to be associated with long-term mortality in AHF. Serelaxin was well tolerated with no notable difference in the overall AE profile; a lower rate of AEs related to renal impairment in the serelaxin treatment arm compared with placebo was noted.

Based on these data, serelaxin represents a new treatment option in AHF, in addition to standard therapy, that may provide rapid and sustained dyspnea relief and improvement of other symptoms and signs of congestion. The findings obtained suggest serelaxin holds promise as the first evidence-based therapy for AHF to substantially improve patients' symptoms and clinical outcomes, including death.

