Renal deterioration will be assessed as the proportion of patients with an increase of ≥ 0.3 mg/dL from screening in serum creatinine levels. Absolute frequencies and proportions of patients with renal deterioration at each day until Day 5, at discharge and at Day 14 in each treatment group will be provided, together with standard errors, asymptotic (Wald) and exact (Clopper-Pearson) confidence limits. The rate of renal deterioration in the two groups will be compared by means of Chi square test at each time point. In case of cell frequencies less than 5, Fisher Exact test will be used.

Index length of hospital stay

Index length of hospital stay (in hours) will be defined as the index discharge date and time minus the index hospitalization start date and time.

Subjects still in the hospital at Day 30 will be censored at the end of Day 30. Subjects who die during the initial hospitalization will be assigned the maximum length of stay (including those censored at Day 30) plus 24 hours. Treatment groups will be compared using a Wilcoxon rank-sum test. Descriptive statistics by treatment group will be presented. Analysis will be done overall and by location (e.g. ICU, CCU, cardiology department).

Death through Day 30

The time (in days) from randomization to the event will be used for analysis. Subjects without an event will be censored at the earlier of the last contact date or Day 30. Treatment groups will be compared using a generalized Wilcoxon test. The Kaplan-Meier estimates of the survival functions for each treatment group will be plotted.

Re-hospitalization post-discharge

The number of re-hospitalizations per patients by treatment group will be described. Treatment groups will be compared using a Wilcoxon rank-sum test. The number of patients with 1, 2, ≥ 2 re-hospitalization will be summarized and treatment groups will be compared with a Chi-Square test. In case of cell frequencies less than 5, Fisher Exact test will be used.

Time to first re-hospitalization (in days) will be defined as the re-hospitalization date minus the randomization date. Subjects still in hospital at Day 30 will be censored at Day 30. Subjects who die when not hospitalized will be assigned as the date of death as their time to re-hospitalization. Treatment groups will be compared using a generalized Wilcoxon test. The Kaplan-Meier estimates for each treatment group will be plotted. Descriptive statistics by treatment group will be presented.

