The time (in days) from randomization to the event plus 1 day will be used for analysis. If death occurred, date is reported in the dedicated eCRF sections “Death – (Endpoint to be adjudicated)” or “Death – (NOT to be adjudicated)”. Subjects without an event will be censored at the earlier of the last contact date (Last known date patient alive in “Survival Information” section) or Day 30. Subjects without any information after baseline will be considered censored at 1 day.

Table 5.2-7: Censoring and time rules

		Status	Time
Death occurred:			
	Difference between date of death and date of randomization +1 day >30 days	Censored	30 days
	Difference between date of death and date of randomization +1 day ≤30 days	Event	Calculated difference
No death occurred:			
	Difference between date of last survival status* and date of randomization +1 day >30 days	Censored	30 days
	Difference between date of last survival status* and date of randomization+1 day ≤30 days	Censored	Calculated difference

* Last survival status is the last known date patient was alive

Treatment groups will be compared using a generalized Wilcoxon test. The Kaplan-Meier estimates of the survival functions for each treatment group will be plotted and summarized.

Re-hospitalization post-discharge

Patients not discharged from the index hospitalization will not be included in the summary of number of re-hospitalizations.

The number of re-hospitalizations per patient by treatment group will be described. Treatment groups will be compared using a Wilcoxon rank-sum test.

The number of patients with re-hospitalization will be summarized. Categories of patients' number of re-hospitalizations will be 0, 1, 2, >2, and will be compared between treatment groups with a Chi-Square test. In case of cell frequencies less than 5, Fisher's Exact test will be used. Cochran-Armitage Test for trend will also be performed.

Statistical Analysis Plan

Sponsor: NOVARTIS

Protocol number: CRLX030A3301

Patients not discharged from the index hospitalization will be included in the analysis of time to first re-hospitalization.

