Time to first re-hospitalization (in days) will be defined as the first re-hospitalization date (Date of admission in "Rehospitalization Information") minus the randomization date plus 1 day. Subjects still in hospital at Day 30 will be censored at Day 30, calculated as randomization date + 30 days. Subjects who die after index hospitalization discharge or when not hospitalized will be assigned the date of death as their time to re-hospitalization. Similarly, subjects who died during index hospitalization without being discharged will have their date of death as their time to re-hospitalization.

Table 5.2-8: Censoring and time rules

	Status	Time
Patient not discharged from index hospitalization at Day 30	Censored	30 days
Patient not discharged but who died during index hospitalization:		
Difference between date of death and date of randomization +1 day >30 days	Censored	30 days
Difference between date of death and date of randomization +1 day \leq 30 days	Event	Calculated difference
Patient discharged from index hospitalization and with at least one re-hospitalization:		
Difference between date of first re-hospitalization and date of randomization +1 day >30 days	Censored	30 days
Difference between date of first re-hospitalization and date of randomization +1 day \leq 30 days	Event	Calculated difference
Patient discharged from index hospitalization but without re-hospitalization:		
Difference between date of last visit* and date of randomization +1 day >30 days	Censored	30 days
Difference between date of last visit* and date of randomization +1 day \leq 30 days	Censored	Calculated difference
Patient discharged from index hospitalization but who died without re-hospitalization:		
Difference between date of death and date of randomization +1 day >30 days	Censored	30 days
Difference between date of death and date of randomization +1 day \leq 30 days	Event	Calculated difference

* Last visit includes date of last visit (if subject is alive at the study termination)

Treatment groups will be compared using a Gehan's generalized Wilcoxon test. The Kaplan-Meier estimates for each treatment group will be plotted. Descriptive statistics by treatment group will be presented.

	<h2 style="margin: 0;">Statistical Analysis Plan</h2>
	Sponsor: NOVARTIS Protocol number: CRLX030A3301

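### Re-hospitalization counts are compared with no allowance for days at risk after discharge, so a difference in index stay alone can look like a difference in readmission

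*SAP*

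**What the plan says.** The relevant text is SAP 5.2, under the heading on re-hospitalization after discharge.

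**Counts.** Patients who never leave the index stay are left out. For the rest: "The number of re-hospitalizations per patient by treatment group will be described. Treatment groups will be compared using a Wilcoxon rank-sum test". The categories 0, 1, 2 and more than 2 are compared by chi-square or Fisher test, with a Cochran-Armitage trend test. No offset, rate or follow-up time is mentioned. Protocol 9.5.1 names the same rank-sum and chi-square (or Fisher) tests.

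**Time to first.** Here "Patients not discharged from the index hospitalization will be included in the analysis of time to first re-hospitalization". Time is the first readmission date "minus the randomization date plus 1 day", the same origin as Protocol 9.5.1: "Time to first re-hospitalization (in days) will be defined as the re-hospitalization date minus the randomization date". For long stays, "Subjects still in hospital at Day 30 will be censored at Day 30, calculated as randomization date + 30 days". Deaths count as events, including those in the index stay: "subjects who died during index hospitalization without being discharged will have their date of death as their time to re-hospitalization". For the test, "Treatment groups will be compared using a Gehan's generalized Wilcoxon test".

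Both are secondary efficacy analyses, with two-sided p below 0.05 called significant and no multiplicity adjustment. Protocol 1.1 reports that in the earlier phase III trial serelaxin "significantly reduced WHF episodes through Day 5 and the overall length of index hospital stay", without giving a number of days.

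**The concern.** A patient can be re-hospitalized only after leaving the index stay. In a 30-day study, someone discharged on Day 3 has 27 days in which to be readmitted, and someone discharged on Day 28 has 2. The count tests treat the two alike. A patient who dies or is lost the day after discharge scores 0 re-hospitalizations, the same as one who stays well for the remaining weeks. The time-to-first analysis deals with such patients through Table 5.2-8 (death is an event, and others are censored at the last visit). The count analysis has no counterpart.

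This would be harmless if discharge times were sure to be balanced. They are not: length of stay is itself a secondary objective, and the sponsor has reason to expect a difference. Treatment is open to site staff (Protocol 5.4), and blood pressure monitoring after the infusion is more intensive on serelaxin (Protocol 6.5.2), so an imbalance could run in either direction. A shorter stay would make serelaxin look worse on readmission counts, and a longer one would make it look protective, with no change in daily readmission risk.

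**Working it through.** **Inputs from the documents.** 3,183 patients at 2:1, so 2,122 on serelaxin and 1,061 on SOC; 30-day horizon; two-sided 5% level. The plan gives no rate or effect size for re-hospitalization, so there is no figure of its own to reproduce.

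**Assumptions, not from the documents.** Stay after randomization, readmission hazard, death hazard, and the stay difference between arms. The post-discharge readmission hazard is identical in both arms throughout.

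**Step 1: by hand.** Take 20 days at risk on SOC, 22 on serelaxin, and 0.006 readmissions per day.
- Expected counts are in the ratio 22/20 = 1.10.
- Proportion readmitted: 1 − exp(−0.006 × 20) = 11.3% against 1 − exp(−0.006 × 22) = 12.4%.
- Pooled proportion about 0.1202; null standard error √(0.1202 × 0.8798 × (1/1061 + 1/2122)) = 0.0122; alternative standard error 0.0121.
- Chance of a significant result against serelaxin: Φ((0.0106 − 1.96 × 0.0122)/0.0121) = 13.4%, where a test unaffected by stay would give 2.5%.
- The same formula at 21 days against 20 gives 6.3%.

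**Step 2: simulation with deaths.** 1,000 trials per row, lognormal stay with median 8 days, death hazard 0.0015/day unless stated. The Monte Carlo standard error near 5% is √(0.05 × 0.95/1000) = 0.7 points.

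| Readmission hazard per day | Stay shorter on serelaxin by | Readmitted among discharged, serelaxin vs SOC | Mean count ratio | Count Wilcoxon rejects | Rate per day at risk rejects |
|---|---|---|---|---|---|
| 0.006 | 0 days | 11.5% vs 11.5% | 1.00 | 5.0% | 4.6% |
| 0.006 | 1 day | 12.0% vs 11.6% | 1.04 | 6.6% | 4.3% |
| 0.006 | 2 days | 12.5% vs 11.5% | 1.09 | 10.2% | 3.7% |
| 0.006 | 3 days | 13.0% vs 11.6% | 1.13 | 19.1% | 4.4% |
| 0.010 | 1 day | 19.1% vs 18.4% | 1.04 | 9.1% | 4.8% |
| 0.010 | 2 days | 19.8% vs 18.4% | 1.09 | 16.7% | 5.8% |
| 0.006, front-loaded | 2 days | 12.0% vs 11.4% | 1.06 | 7.7% | 5.3% |
| 0.004, death 0.006 in hospital, 0.001 after | 2 days | 8.6% vs 8.0% | 1.08 | 7.6% | 4.1% |

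At 0.006/day and 2 days, 10.0 of the 10.2 points are against serelaxin. The chi-square test on counts is less affected (6.6% in that row, 12.4% at 3 days).

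**Step 3: other stay models.** With gamma-distributed stay, no deaths and 20% readmitted per 30 days out of hospital (−ln 0.8/30 = 0.0074/day), the count Wilcoxon test rejects 7 to 8% at 1 day and 15% at 2 days. At 30% per 30 days it rejects 20% at 2 days. A separate run with deaths gave 8% at 1 day and 12% at 2 days, with 4 to 6% for a rate per day at risk.

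**Step 4: time to first, by Table 5.2-8.** With a 2-day shorter stay and 0.006 readmissions per day, the Gehan test rejects 14.2% when in-hospital death is 0.0015/day, and 7.7% when it is 0.003/day (0.001 after discharge). In the last row of the table it rejects 6.0%, with event proportions of 14.6% and 14.7%. The lean seen at low mortality therefore disappears as in-hospital mortality rises, while the count comparison still leans against the arm discharged earlier.

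**The case against.** The best defence is that the tests are valid for what they measure. If serelaxin changes neither stay nor readmission, the count test holds its size (5.0% above). If stay shortens, more patients really are readmitted by Day 30. This holds for a tally by Day 30. But the section is headed as post-discharge re-hospitalization, and by dropping undischarged patients the count test has already given up the full randomized comparison. It is left as a post-discharge measure without post-discharge time.

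Three further points stand. The size depends wholly on an unstated stay difference, and at 1 day it is small. An offset model still conditions on discharge, although no more than the planned test does. Re-hospitalization on its own is not a listed objective (the listed one is the Day 14 composite), the tests are unadjusted secondary ones, and length of stay and Day 30 death are reported beside them.

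A reader might go further and infer that the time-to-first analysis is biased in the same way, because index-stay days are event-free by construction. The documents do not support that. Death in the index stay is an event, so those days are at risk of the event as defined. SAP 5.1 sets randomization as the origin for all time-to-event analyses, and this keeps the randomized comparison. Nor do the documents support a prediction that serelaxin will look worse: no stay difference is given for this trial.

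**Conclusion.** The concern holds for the count comparison. Raw re-hospitalization counts among discharged patients mix readmission risk with time available to be readmitted. At equal daily risk, two-sided rejection by the rank-sum test is about 7 to 8% for a 1-day difference in mean stay and about 8 to 15% for 2 days. It ranges from roughly 6 to 9% and up to 17 to 20% respectively when the assumed readmission pattern is varied. All of these figures rest on assumed stay, readmission and death patterns.

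The time-to-first analysis is sound as a randomized comparison of re-hospitalization or death by Day 30. Its label should say so, and it should be read next to length of stay because readmission cannot occur during the index stay. These are unadjusted secondary analyses, and the primary endpoint is not touched.

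**What to change.** In SAP 5.2:

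1. Make the between-arm comparison of counts a rate comparison, by negative binomial or robust Poisson regression. Use as offset the log of days from index discharge to the earliest of death, last contact or Day 30, and count readmissions over that same window.
2. Keep raw counts and the 0, 1, 2, more-than-2 categories as descriptive tables, without tests.
3. Keep the Table 5.2-8 analysis from randomization. Rename it time to first re-hospitalization or death, and state that it is to be interpreted alongside index length of stay.
4. Optionally add days alive and out of hospital through Day 30 in all FAS patients as a supplementary measure. It should not become the readmission comparison: with equal post-discharge readmission hazard and a 1- to 2-day difference in stay, simulated Wilcoxon rejection was 98 to 100%, driven by stay alone, so it would largely repeat the planned length-of-stay test.

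The cost is SAP wording and a little programming before database lock, plus a note of the departure from the tests named in Protocol 9.5.1. Discharge, readmission, death and last-known-alive dates are already on the eCRF.

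The limits are modest. The model still conditions on discharge. A constant-rate offset corrects slightly too far if readmissions cluster soon after discharge (median rate ratio 0.98 in the front-loaded 2-day setting, rejection 5.3%). The simulations used a simple rate ratio; the negative binomial model itself was not run.

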The number of re-hospitalizations per patient post-discharge will be described.

The time to first re-hospitalization (in days) will be defined as the first re-hospitalization admission date minus the randomization date + 1 day.

Health-related Quality of Life

The EQ-5D-5L is a widely used, self-administered questionnaire designed to assess health status in adults. The measure is divided into two distinct sections. The first section includes one item addressing each of five dimensions (mobility, self-care, usual activity, pain/discomfort, and anxiety/depression). The second section of the questionnaire measures self-rated (global) health status utilizing a vertically oriented visual analogue scale where 100 represents the “best possible health state” and 0 represents the “worst possible health state”.

In this study, the first administration of the EQ-5D-5L questionnaire occurs at baseline visit. If, for whatever reason, the patient is not able to fill in the questionnaire at baseline, it is possible to collect retrospectively these data on Day 2. If this is the case, on Day 2, two questionnaires need to be filled in at this visit: the first one asking the patient to retrospectively describe how he/she felt on the day of admission, and the second one asking the patient to describe how he/she feels today. A special permission was provided by EuroQoL for the use with 2-day recall of the questionnaire.

The EQ-5D-5L quality of life assessment is completed by all study patients (both serelaxin and SOC groups) at baseline (i.e., randomization), at Day 2, at Day 5, at discharge, and at Day 14 post randomization.

Resource utilization

Analyses will be undertaken, as appropriate, to assess the effects of treatments on healthcare resource utilization (RU) parameters.

Throughout the index hospitalization, the level of healthcare resource utilization shall be assessed by the overall length of stay, length of time in specific inpatient care units and procedures rendered during hospital stay. In addition, number of re-hospitalizations (events), number of patients with 1, 2, 3 re-hospitalization(s) and time to first (and recurrent) re-hospitalization(s) (in days) will be evaluated.

Moreover, the details about emergency/urgent care >24 hours not resulting in admission, including tests performed, will be provided.

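### The SAP's time to first re-hospitalization is an unlabelled composite of re-hospitalization or all-cause death, and its companion count is conditional on discharge alive, so neither gives a clean randomized comparison of re-hospitalization

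*SAP*

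**What the plan says.** SAP 4.1 defines the variable by an admission: "The time to first re-hospitalization (in days) will be defined as the first re-hospitalization admission date minus the randomization date + 1 day". SAP 5.2, under the heading on post-discharge re-hospitalization, then sets the rules for patients who are never readmitted.

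- **Death before discharge.** The text reads: "Similarly, subjects who died during index hospitalization without being discharged will have their date of death as their time to re-hospitalization". The Table 5.2-8 row "Patient not discharged but who died during index hospitalization" gives status Event if the death falls within 30 days.
- **Death after discharge without readmission.** The row "Patient discharged from index hospitalization but who died without re-hospitalization" is also an Event within 30 days.
- **Still in hospital at Day 30.** The row "Patient not discharged from index hospitalization at Day 30" is censored at 30 days.

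The two analyses use different populations. For the time analysis: "Patients not discharged from the index hospitalization will be included in the analysis of time to first re-hospitalization". For the count analysis (Wilcoxon rank-sum, chi-square or Fisher, Cochran-Armitage): "Patients not discharged from the index hospitalization will not be included in the summary of number of re-hospitalizations".

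Protocol 9.5.1 has a narrower rule for deaths: "Subjects who die when not hospitalized will be assigned as the date of death as their time to re-hospitalization". It says nothing about death during the index stay and does not restrict the count to discharged patients. SAP 5.1 states that the data are analysed according to Section 9 of the protocol. SAP 5.2 gives no reason for either addition.

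**The concern.** A patient who dies during the index stay has not been discharged and cannot be readmitted, yet contributes an event to a curve and a test reported as re-hospitalization. If serelaxin changes early mortality and does nothing to readmission, the result can still be read as an effect on readmission. SAP 4.1 also lists time to first re-hospitalization among the resource-use measures, where calling a death a readmission would be misleading.

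The count analysis does not repair this. It removes the same deaths, and also the patients alive and undischarged at Day 30, by selecting on discharge alive. Discharge happens after randomization and may depend on treatment. A reader of the clinical study report would thus have two tests under one heading, treating the same death in opposite ways, with neither comparing re-hospitalization cleanly between the randomized groups.

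Secondary comparisons are tested at two-sided 0.05 without adjustment (SAP 5.2). The same mortality difference could therefore appear in several results and be taken for separate benefits.

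**Working it through.** **1. Patient paths.** Applying Table 5.2-8 and the count rule to each possible course:

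| Course | Time analysis | Count analysis |
|---|---|---|
| Dies in index stay within 30 days | Event at death | Excluded |
| Alive, undischarged at Day 30 | Censored at 30 days | Excluded |
| Discharged, dies by Day 30 without readmission | Event at death | Included, zero |
| Discharged, readmitted by Day 30 | Event at admission | Included, at least one |
| Discharged, alive, not readmitted | Censored | Included, zero |

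Every death within 30 days without readmission is an event. That is the definition of a composite of first re-hospitalization or all-cause death. The first and third rows also show that the two analyses treat deaths differently.

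**2. Inputs for size.** Planned size is 3,183 at 2:1 (SAP 2.2, 2.3): 3,183/3 = 1,061 standard of care and 2 × 1,061 = 2,122 serelaxin. The documents state no rate of re-hospitalization or index-stay death, so all rates below are assumptions and there is no stated figure to reproduce.

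**3. Share of events that are index deaths.** Let d be index-stay death, r re-hospitalization among discharged patients and p death after discharge without readmission. The event proportion is d + (1 − d)(r + p).

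- With d = 2%, r = 10%, p = 1%: 0.02 + 0.98 × 0.11 = 0.1278. Index deaths are 0.02/0.1278 = 16% of events.
- Range for d = 1–5% and r = 5–15%, with p = 1%: from 0.01/0.1684 = 6% to 0.05/0.1070 = 47%.

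**4. Apparent effect with r identical in both arms.** Protocol 1.1 reports a 37% mortality reduction through Day 180 in the earlier phase III trial. Applying a ratio of 0.63 to index-stay death is an illustration only. With d = 2% on standard of care, serelaxin has 0.02 × 0.63 = 0.0126, and the event proportion is 0.0126 + 0.9874 × 0.11 = 0.1212. The ratio is 0.1212/0.1278 = 0.95. Over the range in step 3 it runs from 0.98 to 0.84.

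**5. Chance of a significant result.** Simulation of the Gehan test on the Table 5.2-8 scoring: 3,000 trials, deaths on Days 1–12, readmissions on Days 8–30, re-hospitalization 10% in both arms, two-sided 0.05. Ranges are across repeat runs.

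| Index death, standard of care v serelaxin | Significant |
|---|---|
| 3% v 3% | 5–6% |
| 3% v 2% | 12–14% |
| 3% v 1.5% | 23–27% |

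With index deaths not scored as events, the figure stays at 4–5%. The event-proportion ratios here are (0.02 + 0.10)/(0.03 + 0.10) = 0.92 and (0.015 + 0.10)/(0.03 + 0.10) = 0.88.

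A second simulation used the 0.63 ratio, r = 10%, p = 0 and 1,000 trials per setting. It found significance in favour of serelaxin in about 10%, 15% and 31% of trials for d = 2%, 3% and 5%. With index deaths removed as events this was 1–3%, against a nominal 2.5% in that direction.

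**The case against.** Counting death as an event is a recognised, pre-specified way to handle a competing risk, and simply censoring deaths could be informative. The protocol already does it for deaths outside hospital, is silent on index-stay deaths, and leaves analysis detail to the SAP. The SAP therefore extends the protocol rule without contradicting it. Death through Day 30 has its own analysis, and the Day 14 composite is broken down by event type, so a mortality difference would not be hidden. All of this stands. It limits the point to the label, the missing analysis of re-hospitalization itself, and the need to align the two documents.

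Four stronger readings are tempting, and the documents do not support them.

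- *That neither analysis measures re-hospitalization.* The count analysis and the tables of re-hospitalization characteristics in SAP 5.2 use actual readmissions, with discharged patients as the stated denominator for the patient-level percentages. Their weakness is the conditioning on discharge alive.
- *That the 12–14% and 23–27% are false-positive rates.* They assume a real mortality difference, so the null for the composite is false and rejecting it is correct. What would be wrong is to call the result a readmission effect.
- *That the Gehan weighting makes this much worse because index deaths come early.* In a matched simulation Gehan was significant in 14.1% and log-rank in 13.2% of trials at 3% v 2%, and in 26.8% and 25.5% at 3% v 1.5%. The difference is about one percentage point.
- *That a shorter stay gives treated patients more days in which to be readmitted, and so biases the count.* The direction is plausible, but the documents give no expected stay difference from which to size it.

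**Conclusion.** The point holds as one of labelling and interpretation. Table 5.2-8 specifies time to first re-hospitalization or all-cause death through Day 30 and calls it re-hospitalization, with a death rule wider than Protocol 9.5.1. The count tests measure real readmissions, but only in patients discharged alive.

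On the assumed rates, index deaths are roughly 6–47% of the events. A mortality difference of 3% v 2% or 3% v 1.5% gives a significant result in about 12–14% or 23–27% of trials with no effect on readmission. These figures depend wholly on the assumed rates and event timings.

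The consequences are limited. Re-hospitalization after discharge is one of several unadjusted secondary comparisons, and neither the primary endpoint nor the stated objectives are affected.

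**What to change.** In SAP 5.2 and Table 5.2-8:

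1. Rename the analysis as time to first re-hospitalization or all-cause death through Day 30, and reconcile its death rule with Protocol 9.5.1.
2. Add re-hospitalization itself in the full analysis set as cumulative incidence from randomization, with death as a competing event (Aalen-Johansen estimate, Gray's test). Read it beside the planned analysis of death through Day 30, because more early deaths would by themselves lower this incidence.
3. Label the count comparison as conditional on discharge alive.

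Never-discharged patients should not be put into the count with zero re-hospitalizations. That would give death in hospital the best rank in the Wilcoxon test, so that excess early deaths would look like fewer readmissions.

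The dates needed are already collected. The cost is SAP wording and minor extra programming.
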